| | Participants will be instructed to use the device for a minimum of 30 minutes a day. Both M-Stim and LG Smart TENS groups will receive a standard pain management regimen typically used for low back pain standardized across all clinicians participating in the study. Participants will keep the devices and be instructed to use them for pain as needed during the duration of the study. |
| Outcomes | Opioid Use Primary Outcome: |
| | Prior use: For patients with prior or ongoing opioid use, a 30% reduction in MME (Milligram Morphine Equivalents) between the first 14 days and the last 14 days of daily diary recordings using the DOSE data collection tool. |
| | Opioid naïve: 30% reduction of those receiving an opioid prescription "prescribed to me for this event" |
| | Secondary outcomes: Use days; total MME and use past 7 days in the opioid naïve; use days by those with more severe pain using the NIH Research Taskforce definitions; and prescribing compared to a contemporaneous national LBP population (25%). |
| | Pain Primary Outcome: |
| | Chronic: 30% lower disability at 6 months using PROMIS Pain Interference for those with ongoing pain >3 months |
| | Acute: 30% lower NRS 0-10 "pain now" from entry to 10 days for those presenting with an episode of pain starting within the past 2 weeks |
| | Secondary Outcomes: Change in disability for those with >=57.7 PROMIS Pain Interference; restoration of function to normal (PI=50); |

| | integrated analysis with | n common | criteria fo | r restoration | on of function | on with | |
|-------------------------|---|---------------|--------------------|---------------------|----------------------|----------------------------|--|
| | multifidus stimulation s | surgery. | | | | | |
| | | | | | | | |
| Participant Timeline | | Initial Visit | Daily x 28 days | Weekly for 3 months | Monthly for 3 months | Monthly 4 - 6 months | |
| | Consent, Enrollment, Randomization | ALBP, CLBP | | | | | |
| | Minimum Dataset, Pain Catastrophizing Sullivan, PROMIS Depression, Physical Function | ALBP, CLBP | | | | | |
| | NRS (at that moment & past 24 hours) | ALBP, CLBP | ALBP, CLBP | ALBP, CLBP | ALBP, CLBP | CLBP | |
| | NRS after 30 minutes | ALBP, CLBP | | | | | |
| | NRS Past week | | | ALBP, CLBP | ALBP, CLBP | CLBP | |
| | NRS Past month | | | | ALBP, CLBP | CLBP | |
| | PROMIS Pain Intensity, Pain Interference | ALBP, CLBP | | ALBP, CLBP | ALBP, CLBP | CLBP | |

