| Blinding (masking) | Participants were blinded to which device powered the study hypothesis, and blinded to their assigned intervention until after documenting initial NRS pain intensity. Success of blinding the study device (M-Stim) versus the active control (TENS) was tested at months 3-6 with prompts, "select which group you think you were in (control or treatment)" and "How confident are you (0 = Least Confident 100 = Most Confident)." The protocol statistician and study coordinator knew the intervention assignments during enrollment but did not conduct statistical analysis. The PI and treating chiropractor were blinded to allocation during enrollment, with the PI accessing data only after study completion. The analyzing statistician was blinded to device assignment until completion of data cleaning and initial analysis. |
| Data Collection Methods | Site coordinators entered identification and contact information after informed consent on a tablet, then recorded weight, height, and duration to confirm acute or chronic follow-up duration, then participants took the tablet to record pain intensity on a 0-10 NRS now and past 24 hours. While using the device for 30 minutes, participants completed 7-day pain intensity NRS, NIH Back Pain Research Minimum Dataset, including PROMIS measures of Physical Function, Pain Interference, Depression, and Catastrophizing via the Sullivan Catastrophizing scale, Injury Mechanism, prior treatments, exercise and athletic status. |
| | Participants were prompted to record analgesic use, pain, and device use daily for a month on the web-based platform, then weekly, with the monthly surveys adding Pain Interference. All surveys asked about |

analgesic use. Due to the anticipated heterogeneity of opioid formulations, a skip-logic data collection instrument algorithm was created with robust options for Dose per pill (34), Opioid formulations, e.g. hydrocodone, hydromorphone etc. (15) and the Source (DOSE tool, Supplement 2). Sources included "prescribed to me for this event", "prescribed to me for another event", "given to me by a family member", "given to me by a friend", "given to me by an acquaintance or stranger", or "purchased from someone without a prescription". These were converted to a total milligram morphine equivalent (MME) for analysis.

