Participants recorded when they used their device, duration of use, and any additional pain relief modalities (exercise, stretching, bath, hot tub, therapy, massage). Patients were asked to record any thermal use or therapy cycle or channel as appropriate to their device.

Participants verbally endorsing pain for less than three months (acute) were entered into a 3 month follow-up program, or 6 months (chronic) for those for whom back pain had been an ongoing problem for more than 3 months.

Statistical Methods

Statistical analysis was performed with masked intervention allocation by a statistician new to the project to determine differences in primary and secondary outcomes.

An intention-to-treat analysis included all participants meeting inclusion criteria. Summary statistics (means, standard deviations, proportions) were calculated using T-tests and Chi-squared tests. Opioid prescribing differences were calculated with raw percent of change and relative risks. Diary entries and item-level data were analyzed for missing data to assess the need for imputation. Relative risks were calculated for MME and opioid use days between intervention groups, with paired T-tests used to compare first two and last two weeks of MME in those who used opioids during the study. A linear regression assessed BMI's interaction with opioid use, calculating marginal effects with standard errors via the Delta Method. Data analysis was performed using STATANow/SE 18.5.

For pain outcomes, in addition to the above methods, missing 10 day NRS-1 data will be imputed using forward fill and KNN. A neural network will be created to determine factors contributing to 13 week Pain Interference, with iterative modeling to reduce mean absolute error. Graphs with r-squared for predictors will be generated.

| Data Monitoring | Data collection was conducted through an app that tracked daily pain, opioid use and device usage. Monitoring included weekly enrollment review by the protocol statistician to assess comprehension of the data collection tool. Adverse events were reported as per protocol. | |
|------------------------|---|--|

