monthly surveys added past month NRS, Blinding assessment for additional 3 months for those started in chronic strata. Added "source" for each opioid use case to DOSE tool collecting opioid formulation, dose, and number of pills. We intended to use evaluate change in MME over time for chronic opioid users. The FDA recommended requiring participants on opioids maintain dosage and frequency. As we did not have access to prescribing records, and opioid reduction was a desired outcome measure, we evaluated opioid use for the first two weeks versus the last two of those endorsing prior opioid use. We extended the baseline and follow-up Pain Intensity measurements to one month rather than one week. 3a) 8/31/22 – Site Visit. PI noted staff using "will not fit" criteria rather than BMI of 30 from pilot study. New device fits variable BMI, based on abdominal girth. Retained "if device fits", exclusion criteria using BMI changed to BMI >50, noting controversy in using BMI as exclusion criteria. 4) 5/5/23; Added "Do you think you will need surgery" and "do you think you will need epidural" questions, and "did you get surgery" and "did you get an epidural" to monthly. 5) 7/13/2023 New Location added Stratification by chronicity versus opioid use status: enrollment strata were based on verbal endorsement of duration and no acute opioid use for back pain. Initial evaluation of registration data after enrollment was complete revealed 16 of 60 in the "acute" strata reported a duration longer than three months, and half in each chronicity strata no prior opioids for LBP. In consultation with Clinical Trials.gov, we pooled the data and included both opioid and pain outcomes as a single NCT04491175 registry with two different publications and analyses. Informed Informed consent will be obtained from each participant after screening. Consent Participants will be informed about the voluntary nature of the study, with a HIPAA form for confidentiality. Consent will be documented via selecting 'continue' on the digital consent form. Confidentiality Patient data will be stored on password-protected network drives. All data will be de-identified using a unique study ID for each participant. Confidential records will be stored in secure, restricted-access rooms. Declaration of The principal investigator has financial conflict of interest from design interests and research into the DuoTherm device, and creating a company to

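### The MME primary does not say how unrecorded diary days count; if its 14-day value is a sum, waning diary completion alone can produce the 30% reduction

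*Combined protocol and SAP*

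**What the plan says.** All references are to the combined protocol and SAP.

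- **Outcomes.** For participants with prior or current opioid use, the primary outcome is a 30% MME reduction "between the first 14 days and the last 14 days of daily diary recordings using the DOSE data collection tool". Sum or mean is not stated.
- **Participant Timeline.** The diary column is headed "Daily x 28 days", so two 14-day calendar windows abut.
- **Data Collection Methods.** After describing pill doses, formulations and sources, the text says: "These were converted to a total milligram morphine equivalent (MME) for analysis".
- **Statistical Methods.** The first-versus-last change is analysed by "paired T-tests used to compare first two and last two weeks of MME in those who used opioids during the study". Relative risks between groups are named for MME and use days, but no between-arm test of this change is named.
- **Statistical Methods, missing data.** "Diary entries and item-level data were analyzed for missing data to assess the need for imputation". The only imputation methods named belong to a pain outcome: "missing 10 day NRS-1 data will be imputed using forward fill and KNN".
- **Protocol Amendments.** The rationale for the outcome reads: "we evaluated opioid use for the first two weeks versus the last two of those endorsing prior opioid use".
- **Objectives.** The primary objective is a comparison of M-Stim with TENS.

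**The concern.** The outcome depends on a daily self-report diary, and the two windows are its first and second halves. Any drop in completion over the month therefore falls on the second window. If each window is summed, a day with no entry adds nothing and cannot be told apart from a day without opioids. Fewer entries then look like less opioid use, in the direction of the trial's hypothesis and on the scale of its success threshold.

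The planned paired t-test cannot separate the two explanations, because it compares each participant's later window with the earlier one and has no concurrent control. A reported 30% fall could reflect less opioid use, fewer diary entries, or both.

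**Working it through.** **The plan's own figure.** The documents give no completion rate. The one numerical claim for this outcome is 85.4% power with 50 per group (Sample Size). From the cited reductions of 26.2 (SD 32.8) and 5.8 (SD 34.2):

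- Pooled SD = √((32.8² + 34.2²)/2) = 33.51
- d = (26.2 − 5.8)/33.51 = 0.609
- Two-sample t-test, 50 per group, two-sided 0.05: power 85.4%

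The figure reproduces and this point does not alter it. It reproduces as a two-sample comparison, so the sample size fits a between-arm test and not the paired test in Statistical Methods.

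**Apparent change with constant use.** Let c1 and c2 be the share of days recorded in days 1-14 and 15-28 (assumed values). If windows are summed and blanks add zero, the expected apparent reduction is 1 − c2/c1.

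| c1 | c2 | Apparent reduction in total | Change in mean per completed day |
|---|---|---|---|
| 80% | 80% | 0% | 0% |
| 90% | 80% | 1 − 0.80/0.90 = 11% | 0% |
| 90% | 70% | 1 − 0.70/0.90 = 22% | 0% |
| 90% | 63% | 1 − 0.63/0.90 = 30% | 0% |
| 90% | 50% | 1 − 0.50/0.90 = 44% | 0% |

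The 30% threshold is reached whenever c2 is 70% of c1. The last column holds if missingness is unrelated to use.

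**Effect on the tests.** A simulation with no true change used 2,000 replicates per setting. Its assumptions are illustrative: skewed MME between and within participants, use on 70% of days, completion varying between participants, and missingness unrelated to use. Group sizes were 50 per arm (the planned chronic group) and 25 (half of that). Share of runs with p < 0.05:

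- *Within-arm paired t-test on totals.* Completion 95% to 85%: 16% (n = 25) and 29% (n = 50). Completion 95% to 75%: about 51% and 79%. Completion 95% to 66.5%: about 79% and 96%.
- *Same test on the mean per completed day.* 3% to 5% in every setting.
- *Between-arm test of change in totals, equal waning.* About 5%.
- *Between-arm test of change in totals, unequal waning.* With both arms at 95% early and 65% versus 85% late: 27% (n = 25) and 46% (n = 50). The apparent reductions are 1 − 0.65/0.95 = 32% and 1 − 0.85/0.95 = 11%, a gap of 21 percentage points with no true effect.
- *Between-arm test on the mean per completed day, same unequal waning.* About 4% to 5%.

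**Where the mean per completed day fails.** Suppose use at a constant dose on 70% of days, and that in the second window participants skip the diary on exactly the opioid-free days. The true mean is 0.70 of the dose, but the recorded mean is the full dose, an apparent rise of 1/0.70 − 1 = 43%. A sum would be correct here. The alternative therefore needs a sensitivity analysis.

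**The case against.** The strongest reply is that this is a gap in specification and not an error. Several parts of it stand.

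- *A reader might infer that the plan definitely compares 14-day totals.* It does not say so. The word total in Data Collection Methods may mean only that pills, formulations and sources are added into one unit. In Outcomes, total MME is named for a secondary outcome in the opioid naïve. The sum is the natural reading, because no completed-day denominator appears anywhere, but it is an inference. A mean per completed day is also compatible with the text and would not be exposed in this way.
- *A reader might infer that missing diary data were ignored.* They were not: Statistical Methods plans to examine them before deciding on imputation. That is an intention to look, however, with no missing-day rule, minimum number of entries or method for MME.
- *A reader might infer that waning always biases the trial's comparison.* It does not. Equal waning leaves the between-arm error rate at about 5%.
- *A reader might infer overlapping windows, by counting entries instead of days.* Only the Outcomes phrase about diary recordings lends itself to that. Statistical Methods and Protocol Amendments both speak of two weeks, and 28 scheduled days give two windows that do not overlap. Overlap would in any case pull the change towards zero. This is a matter for aligning the wording.

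It is also fair to say that the documents do not show that completion fell, and that the DOSE tool (Supplement 2) is not available here. Whether it records an explicit no-opioid answer cannot be judged.

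**Conclusion.** The point holds in conditional form. The plan leaves open how a primary outcome is calculated, and on the natural reading an unrecorded day counts as no opioid use. A fall in completion to 70% of its early level then meets the 30% threshold without any change in use. The within-person paired t-test is directly exposed; the contrast with TENS is exposed only to unequal waning.

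The size rests on assumed completion rates, constant true use and, for the simulated error rates, an illustrative pattern of use. The documents supply none of these. They do not support the conclusion that a false reduction occurred. They show that the plan as written could not rule one out.

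**What to change.** - Define the windows as calendar days 1-14 and 15-28, and align the Outcomes wording with the two-week wording in Statistical Methods and Protocol Amendments.
- Define the outcome as mean MME per completed diary day. Count an explicit no-opioid entry as zero and an unrecorded day as missing.
- Keep the first-versus-last change, but make the between-arm difference in that change the primary comparison, as the objective asks. Estimate it in a model using all recorded days, with an arm-by-window term and allowance for repeated days within participant. This replaces the within-arm paired t-test.
- Report diary completion by arm and window.
- Add a sensitivity analysis for missingness related to use, including the case where diaries are skipped on opioid-free days.

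The cost is SAP wording and a re-derived variable from data already collected. Participants with few entries get less precise means, and the main analysis assumes that missingness is unrelated to use. Because parts of the plan are written in the past tense, the change should be dated and its timing relative to unmasking stated.

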ClinicalTrials.gov NCT04491175

SPIRIT Table: eProtocol M-Stim for LBP Opioid & Pain Reduction

| Administrative | Description |
|-----------------------|---|
| Title | Multimodal Mechanical Stimulation to Reduce Opioids for Low Back Pain: A Randomized Clinical Trial An Outpatient, Double-blinded Randomized Trial Comparing the Impact of DuoTherm™ Mechanical Stimulation (M-Stim) Versus TENS on Opioid Prescribing and Use for Low Back Pain |
| Trial Registration | ClinicalTrials.gov NCT04491175 |
| Protocol Version | NIH funded protocol submitted 5/29/2019 to FDA Q191165 |
| | IRB Protocol Submission Date: 8/10/2019 |
| | Protocol Amendment Number: 4 |
| | Authors: [name] |
| | Revision Chronology: |
| | 8/10/2019 Original [COVID delay] 4/21/2022 FDA recommended modifications from Q191165 incorporated to protocol: increased sample size to 60 opioid naïve acute (for 3 months) and 100 chronic (with 6 months followup); Replaced Sham with LG Smart TENS and added a blinding assessment; Outcome measures of PROMIS Pain Interference, Pain Intensity, Depression to be measured weekly the first month. 6/8/2022 – Final survey design reduced daily diary reporting to 1 month due to budget constraints of longer follow up. Depression and Catastrophizing only as baseline; weekly NRS Pain Interference (3) PROMIS Pain Interference (2) and Pain Intensity collected until 3 months for all; Monthly surveys added past month NRS, Blinding assessment to monthly survey at 3 months and after for those started in chronic strata. Added "source" for each opioid use case to DOSE tool collecting opioid formulation, dose, and number of pills. 5/5/23; Added "Do you think you will need surgery" and "do you |
| | think you will need epidural" questions, and "did you get surgery" and "did you get an epidural" to monthly. |
| | 5) 7/13/2023 New Location added |

| Funding | National Institute on Drug Abuse, R44DA049631, R44DA058952 |
|--|---|

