| Study Design | Co-Primary Objective, Acute Pain: To determine whether multimodal M-Stim reduces Pain Intensity 30% more than TENS in the first 10 days after presenting for treatment. Co-Primary Objective, Chronic Pain: To determine whether multimodal M-Stim reduces disability 30% more than TENS at 6 months. A randomized, double-blind controlled trial with 3- (aLBP) or 6- month (cLBP) follow-up. |
|-------------------------|--|
| Study Setting | The study will be conducted at mixed physical therapy/chiropractic practices in Washington, DC, Maryland, and Virginia, which offer demographic and economic diversity. These clinics provide an ideal environment, with frequent follow-ups and ongoing therapy but no onsite access to opioid prescribers. |
| Eligibility Criteria | Inclusion Criteria: - Male or female adults aged 18-90 presenting for treatment of acute or chronic low back pain - Self report of moderate to severe LBP of 4 or greater out of 10 on a 0-10 Numeric Rating Scale. - Acute: pain duration <3 months not using opioids for the current exacerbation of low back pain - Chronic: Pain duration >= 3 months with or without ongoing opioid use - Capacity to understand risks and benefits (informed consent). - Smartphone for Qualtrics web-based platform use Exclusion Criteria: - Radicular pain likely reflecting a surgical or mechanical problem - Inability to apply or use the device - Sensitivity to cold or vibration (e.g Raynaud's or Sickle Cell Disease) - Diabetic neuropathy rendering a patient unable to determine if the device is too hot - New neurologic deficits, skin lesions over the low back area - A contraindication to any medication for pain management that would impact analgesic use record |

| | - Pacemaker |
|--------------|---|
| Intervention | The experimental arm DuoTherm is a novel multimodal low back pain relief device incorporating 8 harmonic vibration patterns of mechanical stimulation (M-Stim) including neuromodulatory frequencies, 5 intensity levels, and optional heat, cold, and pressure delivered through a sculpted metal plate attached with a belt and controlled by buttons on the belt. Patients will be instructed to use the device at least daily for 30 minutes. The active control is a prescription 4-lead 8-channel TENS unit (LG Smart) with variable intensity. |

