| | Dose, Opioid formulation, number Source (DOSE tool), other analgesics | ALBP, CLBP | ALBP, CLBP | ALBP, CLBP | ALBP, CLBP | CLBP | |
| | Device usage | | ALBP, CLBP | ALBP, CLBP | ALBP, CLBP | CLBP | |
| Sample Size | To estimate the M-Stim | interventi | on effect : | size, a retro | spective st | udy of | |
| | 59 cLBP patients on ch | ronic opioi | ds (100% | prolonged | opioid use) | | |
| | reported a 28% reducti | on in MME | after spin | al stimulat | or | | |
| | implantation,[40] reducing MME 26.2(SD32.8) compared to 5.8(SD34.2) | | | | | | |
| | for those with conventional treatment (effect size 0.60. A priori, we would | | | | | | |
| | be able to detect an effect size of 1 (meaning a difference of 1 standard | | | | | | |
| | deviation) with 94% power and alpha of .03 using a Wilcoxon Mann | | | | | | |
| | Whitney test with 30 in each group. With this effect size for a two-sided | | | | | | |
| | significance of 0.05, 17 participants per group would detect a 30% | | | | | | |
| | prescribing reduction, while 50 participants on chronic opioids per | | | | | | |
| | treatment group would provide 85.4% power to detect a 30% reduction in | | | | | | |
| | MME. Given the 20% in a previous study by Jamieson et al, we increased | | | | | | |
| | the cLBP sample to 50 | - | | Jannoson | icat, we iiio | ioasea | |
| | | | | | | | |

| | We planned to recruit 60 aLBP participants who had never taken opioids for their back pain, and 100 cLBP without a new prescription but with or without chronic opioid for cLBP. |
|----------------------------|--|
| Recruitment | Patients were recruited from Kaizo Health Centers in Landover and Fairfax, through direct referrals, flyers, and digital content like social posts and emails targeting local populations. Flyers were also distributed at three local pain clinics. |
| Randomization | After eligibility screening and informed consent, a 4-digit participant ID and the intervention allocation were randomly assigned by the survey software to either the DuoTherm or LG Smart TENS group within acute and chronic arms. A copy of the informed consent was emailed to the participant. |

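### As described, the opioid-naive primary outcome counts participants who took an opioid prescribed for this event, not participants who received a prescription, so it cannot support a claim about prescribing.

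*Combined protocol and SAP*

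**What the plan says.** Under Outcomes, the opioid-naive primary is a "30% reduction of those receiving an opioid prescription", identified by the answer that the opioid was prescribed to the participant for this event. Data Collection Methods shows that this answer is one of six options for Source in the DOSE tool. The revision chronology (entry of 6/8/2022) says that Source was added "for each opioid use case to DOSE tool collecting opioid formulation, dose, and number of pills".

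The surveys around the tool are described in terms of use: "Participants were prompted to record analgesic use, pain, and device use daily for a month on the web-based platform, then weekly". The opioid row of the Participant Timeline reads "Dose, Opioid formulation, number Source (DOSE tool), other analgesics". No passage describes a question on whether a prescription was written, received or filled.

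No second source is described. Protocol Amendments states "As we did not have access to prescribing records", and Study Setting says that the clinics have "no onsite access to opioid prescribers".

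The plan still treats prescribing and use as different outcomes. Statistical Methods says "Opioid prescribing differences were calculated with raw percent of change and relative risks". Use days, total MME and past-7-day use are secondary outcomes, and a further secondary compares prescribing with a national low back pain population at 25%.

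**The concern.** Receiving a prescription depends on a prescriber. Taking a pill depends on the participant. If the first is seen only through the second, a prescription that is never filled or never used is not counted.

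This matters because the device is meant to relieve pain, and so to make people less likely to take pills they already have. A fall in the recorded endpoint could then come from less use with no change in prescribing, yet be reported as a prescribing difference. The comparison with the national figure has a further problem: the trial's numerator would need at least one dose taken, while the plan presents the 25% as a prescribing rate.

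**Working it through.** **The plan's own figure.** Sample Size gives 17 per group to detect a 30% prescribing reduction, with an effect size of 1 SD and two-sided alpha 0.05. With 80% power (assumed, since none is stated), a two-sample t-test needs 16.7, rounded up to 17. The figure reproduces, but it has no bearing on how a prescription is ascertained.

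**What is recorded.**

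1. Endpoint: receipt of a prescription for this event (Outcomes).
2. Data item: Source = prescribed to me for this event (Data Collection Methods).
3. Trigger for the item: an opioid use case (revision chronology).
4. Back-up source: none described (Protocol Amendments, Study Setting).

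From 2 to 4, the recorded event is taking at least one opioid prescribed for this event.

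**Model.** Let p be the probability of being prescribed an opioid, and u the probability of using and recording it, given that it was prescribed.

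Recorded rate = p × u

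Recorded RR = (p_M × u_M) / (p_T × u_T), where M is M-Stim and T is TENS. With equal prescribing, p_M = p_T, this reduces to u_M / u_T.

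**Inputs.** p = 25% is the plan's national figure. The documents give no value for u, so every u below is an assumption.

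**Between arms, equal prescribing of 25% (true RR 1.00):**

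| u on TENS | u on M-Stim | Recorded TENS | Recorded M-Stim | RR | Spurious reduction |
|---|---|---|---|---|---|
| 80% | 80% | 0.25 × 0.80 = 20.0% | 0.25 × 0.80 = 20.0% | 1.00 | 0% |
| 80% | 70% | 20.0% | 0.25 × 0.70 = 17.5% | 0.875 | 12.5% |
| 90% | 70% | 0.25 × 0.90 = 22.5% | 17.5% | 0.778 | 22% |

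The RR does not depend on p. At p = 50%, the top of the background range in the protocol, shares of 80% and 70% give 40% against 35%, again RR 0.875. With equal shares the RR is unbiased and only precision is lost.

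**Against the 25% national rate, true prescribing of 25% and the same u in both arms:**

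| u | Recorded rate | Apparent reduction |
|---|---|---|
| 90% | 22.5% | 10% |
| 80% | 20.0% | 20% |
| 70% | 17.5% | 30% |

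This comparison is biased in the devices' favour whenever u is below 100%, with no difference between arms needed.

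**The case against.** **The instrument is not available.** The DOSE tool is in Supplement 2, and its opening question is not described. The Participant Timeline is not a full list of items: the surgery, epidural and blinding questions were in the monthly surveys and have no row. A reader might infer that every survey recorded only opioids taken. The documents do not establish that. They do tie Source to use wherever they describe it, so the point stands subject to Supplement 2.

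**The outcome sits under an opioid use heading, and the primary objective is to reduce opioids.** Fewer people taking opioids would be a real benefit within that objective. This is fair, and it is why restating the endpoint is enough. It does not justify reporting a use measure as prescribing or setting it beside a prescribing rate.

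**Size of the between-arm bias.** A reader might infer that the whole 30% target could be an artefact. Shares of 80% and 56% do give 20% against 14%, RR 0.70, but 56% is simply 80% × 0.70, and nothing in the documents supports it. Nor can one say that the trial would declare such an effect. With 30 per arm (60 acute participants, 1:1 assumed), 20% against 14% reaches two-sided significance about 9% of the time by chi-squared and about 4% by Fisher's exact test.

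**Prescriptions held at entry.** Acute eligibility is worded by opioid use, so someone holding an unused prescription could enter and become an event at the first pill. A reader might take this as a separate bias between arms. Randomisation balances such prescriptions in expectation, and Sample Size already describes the chronic group as having no new prescription. What remains is that some events may rest on prescriptions that predate the device.

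**Conclusion.** The point holds as a mismatch between a primary endpoint and its measurement. As described, the opioid-naive primary measures use of an opioid prescribed for this event. The between-arm relative risk is valid for that quantity. As an estimate for prescribing it is biased only if the share of prescriptions used differs by arm. The direction is plausible, but the documents give nothing to fix the size; 12.5% at 80% against 70% is an illustration. The comparison with the 25% national rate is on firmer ground: it favours the devices at any share below 100%, by 10% to 30% in relative terms for assumed shares of 90% down to 70%.

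The verdict rests on two assumptions: that Supplement 2 has no prescription item independent of use, and that some prescribed opioids go unused. If Supplement 2 does have such an item and the endpoint is derived from it, the point falls away.

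**What to change.** 1. Check Supplement 2 and state in the plan how receipt of a prescription was ascertained.
2. If there is no use-independent item, restate the opioid-naive primary as: took at least one opioid prescribed for this event. Use the same wording in Statistical Methods, and limit the conclusion to use of prescribed opioids.
3. Drop the comparison with the 25% national prescribing rate. If it is kept, state that the trial's figure omits unused prescriptions and show it over a range of assumed use shares.
4. Protocol Amendments says that enrollment is complete, so a new survey item is not the main remedy. Only if data collection is still open, add a yes/no question on whether an opioid was prescribed for this back pain, whether or not it was filled or taken. Include a baseline version where possible, to identify prescriptions that predate the device.

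Steps 1 to 3 need no new data. Their cost is a narrower claim. Step 4 adds one short item per survey, much as the surgery and epidural questions were added to the monthly survey.
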